Section D: Purpose and Objectives

This is an exploratory randomized controlled trial study to test feasibility, acceptability, and proof of concept efficacy of Continuous Diffusion of Oxygen (CDO) adjunct therapy for decreasing healing time and reducing tissue dehiscence post breast reconstruction. We will assess the benefit of this novel adjunct therapy on successful closure, tissue oxygenation, scar appearance, and patients centered outcomes including perception of benefit, pain, sleep quality, and quality of life. Since all procedures are bilateral, an internal randomization will be performed based on breast side (left or right). The patients will be given CDO in one breast defined as intervention breast. A 5x5 cm CDO dressing will be placed by the plastic surgeon over the T-inframammary fold after the Dermabond glue and Prineo tape are placed. Then, Silagen (a silicon sheet) will be placed on top of the CDO dressing to secure it in place. The remaining parts of the incision will be covered with Dermabond Glue and Prineo tape. On the contrary, the control breast will be given the standard dressing (Dermabond + Prineo tape). The study device OxyGeni is a Class II medical device which has US Food and Drug Administration (FDA) 510(k) clearance, CE-Mark approval and a Health Canada license for the treatment of wounds.

Outcomes will be assessed on weekly-basis up to 4 weeks. Here are the aims and hypotheses for this study:

Aim1: To assess effectiveness of CDO adjunct therapy in reducing the likelihood of wound complication post-surgical

closure.

H1: CDO adjunct therapy will reduce the likelihood of surgical wound complication including dehiscence and its volume, infection or surgical revision, compare to standard of care dressing.

Aim2: To assess changes in skin perfusion in patients treated with CDO adjunct therapy.

H2: CDO adjunct therapy will improve tissue oxygen saturation in >50% of the patients as compared to baseline (measurements at baseline, 2 weeks, and 4 weeks).

Aim3: To evaluate changes in quality of life, anxiety during dressing change, and psychosocial parameters in patients with a surgical wound treated by CDO adjunct therapy

H3: CDO adjunct therapy will improve subject quality of life, reduce anxiety, and reduce perceived pain and physiological stress response during dressing change compared to the control group.

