1) Baseline (Surgery Day, Week 0) 2) Visit 1 (Week 1 Post-Op) 3) Visit 2 (Week 2 Post-Op) 4) Visit 3 (Week 3 Post-Op) 5) Visit 4 (Week 4 Post-Op) 6) Visit 5 (minimum of 6 months Post-Op) *optional

Baseline: Subjects will be randomized to internal control. Since all procedures are bilateral, an internal randomization will be performed based on breast side (left or right). The patients will be given CDO in one breast defined as intervention breast. A 5x5 cm CDO dressing will be placed by the plastic surgeon over the T-inframammary fold after the Dermabond glue and Prineo tape are placed. Then, Silagen (a silicon sheet) will be placed on top of the CDO dressing to secure it in place. The remaining parts of the incision will be covered with Dermabond Glue and Prineo tape. On the contrary, the control breast will be given the standard dressing (Dermabond + Prineo tape).

Visits 1-4: All patients will have baseline assessment including visual, dermal, and tissue oxygen saturation level. The status of wound closure and presence of wound complication will be monitored every week. Each subjects will need up to 5 visits including baseline assessment, and weekly assessment up to 4 weeks or full wound healing or surgical revision, whichever comes first. At each visit, patients will be provided standard of care treatment including regular wound dressing change. Table 1 in attachments' section summarizes the key measurement at each study visit. At Visit 4, the CDO therapy will be removed. Subjects will then have the option to return at minimum 6 months later for a final follow-up visit listed below.

Visits 5: Optional follow-up visits. This visit can also be done remotely should the person not be available to attend the clinic.

Inclusion Criteria:

18-85 years of age. Ability to provide informed consent. Presence of a wound due to surgical intervention and closure. Subject or responsible caregiver is willing and able to maintain the required Continuous Diffusion of Oxygen (CDO) system (if assigned to the intervention group) and applicable dressing changes

Exclusion Criteria:

Active Drug/alcohol abuse (or history of drug/alcohol abuse in last 1 month); excessive lymphedema; presence of active infection; subject has a history of or any intercurrent illnesses or conditions that would compromise the safety of the subject according to judgement of a qualified wound specialist.

F2. Procedure

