Wound Assessment (primary outcome): A digital photo/video of wound will be taken for wound size verification, estimation of wound size, success of wound healing, and determination of wound dehiscence. Measurement will be performed at every visit.

Pain Intensity Assessment (VAS) (secondary outcome): The subject will be provided with a numeric pain scale where he/she will report pain intensity. Research staff will document subject's pain level. (Collected at every visit)

Adverse Event Reporting: Research Staff will document and report any study/non study related incident as per institution regulations. (Collected at baseline and visits 1-4)

Device Acceptability Questionnaire: To determine patient perception of benefit, perceived ease of use, and attitude toward the use of device, we will use a technology acceptance model (TAM) questionnaire tailored for the purpose of this study. This assessment will be done at the conclusion of the study (week-4)

Questionnaires (optional): Quality of Life (PROMIS), functional status, Frailty Status (TSFI), Cognitive Assessment, and Sleep Quality (PSQI). To evaluate functional status, we will use well accepted and validated general functional assessment instruments. PFIBS for Pain Frequency, Intensity and Burden Scale, MOCA for Mental Exam, and Visual analog scale for pain. (All questionnaires are optional and may be done at any study visit upon time availability and patient acceptability). We will add the already approved questionnaires for the parent study, which include pain. Additionally, we will include Likert Scales (Moon SH et al, 2011; Singer AJ et al 1997; Hollander JE et al 1995; and Ridway DM et al 2007) and Patient Attitude to Scarring Scale (PASS, Kantor J et al 2016) and Patient and Observer Scar Assessment Scale (POSAS) to assess the following patient-reported outcomes: patient satisfaction and cosmetic appearance to evaluate scar itchy, perception of scar thickness, scar discomfort, and pain for each wound side (i.e., left and right breast). SCAR may be used to assess plastic surgeon satisfaction with the scarring. These questionnaires will be answered to the best of the participant's abilities. Should the participant lack certain capacities that make it difficult for them to respond to these questionnaires, they will not be conducted with that participant.

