The primary outcomes of this study are 1) tissue oxygen saturation level measured using Kent Imaging system and 2) incident of wound related adverse events (e.g., incident wound dehiscence, infection, scar size, and surgical revision). Secondarily outcomes include pain, wound outcomes (e.g. wound size, scar size, wound healing rate, etc assessed using digital photography), area of inflammation (assessed using KENT), and pain (assessed using VAS). Exploratory outcomes include patient quality of life, sleep quality, anxiety, and depression. Baseline between group comparison will be dine using two-sample t-tests, Mann-Whitney U-test, or Chi-square depend on scale/distribution of the variables (i.e., parametric, non-parametric, or binary). We will use general mixed linear model and post-hoc analysis to examine difference between

groups (time, group, and time X group effect) for skin perfusion. We will adjust the results based on baseline incision wound size and duration between baseline and last visit assessment. Subjects with at least one week continue treatment will be included in the analysis. Controlled variables include age, BMI, baseline vascular health. We will use chi-square to estimate whether the number of wound complication incidents is less in the intervention group compared to the control group. Chi-square or repeated ANOVA or Mann-U test depend on scale/distribution of the variable will be used for secondary and exploratory outcomes.

Section H: Potential Risks/Discomforts

H1. Potential Risks/Discomforts

Describe and assess any potential risks/discomforts; (physical, psychological, social, legal, or other) and assess the likelihood and seriousness of such risks:

As any new investigational device, there are some risks, which are anticipated to be minimal in this study. Some of potential risks could be: * Skin related discomfort, erythema (redness), skin rash, dryness and itching. * Skin allergic reaction to dressing adhesive. * Tenderness/minor ache around the dressing application area * Heat sensation and/or perspiration with wearing dressing * Some impairment of mobility due to dressing unit

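### Breast side is randomised within each patient, but G2 tests the primary complication outcome by chi-square between groups and names no paired test for binary outcomes

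*Combined protocol and SAP*

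**What the plan says.** Section D and the Baseline paragraph of F1 set up a split-body design: "Since all procedures are bilateral, an internal randomization will be performed based on breast side (left or right"). Both add: "The patients will be given CDO in one breast defined as intervention breast". The other breast of the same patient receives the standard dressing.

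G2 makes wound-related adverse events one of two primary outcomes. The test is: "We will use chi-square to estimate whether the number of wound complication incidents is less in the intervention group compared to the control group". The mixed linear model in the same section is stated for skin perfusion only. For the remaining outcomes: "Chi-square or repeated ANOVA or Mann-U test depend on scale/distribution of the variable will be used for secondary and exploratory outcomes". Some of those outcomes are recorded per breast. The optional questionnaires in F2 include "scar discomfort, and pain for each wound side (i.e., left and right breast").

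G2 includes only subjects with at least one week of treatment. It states no alpha, no sidedness and no interval for the complication outcome. G1 bases the 30 patients on budget and feasibility, with no power calculation.

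**The concern.** An ordinary chi-square treats the 30 CDO breasts and the 30 control breasts as 60 independent observations. They are two breasts of the same women, who share age, BMI, smoking, comorbidity and surgeon. If complications on the two sides are correlated, the test uses the wrong variance for the difference, so its p-value and any interval built on the same assumption are wrong.

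The unpaired table also loses the number of discordant pairs. G1 leaves open a later increase in sample size after initial results, and a paired extension would be sized on that number. The same fault arises for a per-breast secondary outcome if the analyst takes the chi-square or Mann-Whitney option.

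**Working it through.** **No figure of the plan to reproduce.** The sample size has no calculation behind it.

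**Inputs from the documents.** 30 patients (F1, G1), one CDO and one control breast each. Section C puts poor healing outcomes and adverse events at 10-15%, but covers a wider set of outcomes than the primary and does not say whether the figure is per breast or per patient.

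**Assumptions.** That range is used as the rate per breast, p. Left-right correlation ρ runs from -0.1 to 0.6. The test is two-sided at 5%, although G2's wording is directional. The effect is a halving of the rate.

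**Large-sample reasoning.** Under no effect, the true variance of the risk difference is 2p(1-p)(1-ρ)/n. Chi-square assumes 2p(1-p)/n. Its true size is therefore about 2Φ(-1.96/√(1-ρ)):
- ρ = 0.4: 1.96/√0.6 = 2.53, size about 1.1%.
- ρ = 0: 5%.
- ρ = -0.1: 1.96/√1.1 = 1.87, size about 6.2%.

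**Exact check.** Let a be the patients affected on both sides, b on the control side only, c on the CDO side only, and d on neither. All tables with a+b+c+d = 30 were enumerated with multinomial probabilities. The both-sides probability is p_C·p_T + ρ√[p_C(1-p_C)p_T(1-p_T)]. Chi-square is Pearson's statistic without continuity correction on a+b of 30 against a+c of 30. Asymptotic McNemar is (b-c)²/(b+c) on 1 degree of freedom.

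Null rejection:

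| ρ | Chi-square, 10% / 15% | Asymptotic McNemar, 10% / 15% | Exact McNemar, 10% / 15% |
|---|---|---|---|
| 0 | 5.4% / 5.3% | 4.8% / 4.5% | 1.0% / 1.8% |
| 0.2 | 3.2% / 3.2% | 4.6% / 4.8% | 0.6% / 1.3% |
| 0.4 | 1.4% / 1.5% | 3.4% / 4.7% | 0.3% / 0.7% |
| 0.6 | 0.4% / 0.4% | 1.6% / 3.2% | 0.1% / 0.2% |

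At ρ = -0.1 chi-square rejects in 6.7% (10% rate) and 6.4% (15% rate).

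Power for a halving:

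| Effect | ρ | Chi-square | Asymptotic McNemar | Exact McNemar |
|---|---|---|---|---|
| 15% to 7.5% | 0 | 15.7% | 13.6% | 5.6% |
| 15% to 7.5% | 0.4 | 9.5% | 18.2% | 4.1% |
| 15% to 7.5% | 0.6 | 6.1% | 19.0% | 2.8% |
| 10% to 5% | 0 | 10.6% | 9.9% | 2.0% |
| 10% to 5% | 0.4 | 5.2% | 9.0% | 1.0% |

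For 15% to 7.5% at ρ = 0.4, 9.2% of trials are significant by asymptotic McNemar only and 0.5% by chi-square only. At ρ = 0 the shares are 1.1% and 3.3%.

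**Single data sets can go either way.**
- Five control against one CDO event, with one patient affected on both sides (a=1, b=4, c=0): chi-square p = 0.085, asymptotic McNemar p = 0.046, exact p = 0.125.
- Six against one, with no patient affected on both sides (a=0, b=6, c=1): 0.044, 0.059 and 0.125.

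**Point estimate.** (a+b)/30 - (a+c)/30 = (b-c)/30. The pairing cancels, so the estimated difference is the same.

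**Interval width, large-sample.** At 15% on both sides and ρ = 0.4 the half-width is 1.96√(0.255/30) = 18.1 points unpaired and 1.96√(0.153/30) = 14.0 paired. The intervals that correspond to the two tests show a smaller gain. The unpaired score interval covers 98.5% with mean half-width 18.9 points; the paired score (Tango) interval covers 95.3% with 16.4.

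**Secondary outcomes.** This applies only if Mann-Whitney is the option chosen. For a continuous per-breast outcome with a 0.5 SD difference and ρ = 0.3 / 0.5 / 0.7, simulated power is 45 / 44 / 44% by Mann-Whitney and 59 / 74 / 92% by Wilcoxon signed-rank.

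**The case against.** **McNemar is itself a chi-square statistic, so the text may already mean it.** This is possible, but nothing supports it. G2 describes two groups and names no pairing. The same section plans independent-sample methods for patients who serve as their own controls: "Baseline between group comparison will be dine using two-sample t-tests, Mann-Whitney U-test, or Chi-square depend on scale/distribution of the variables". Those baseline tests do not affect the primary result, but they show how the section is thinking.

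**The plan is not blind to pairing.** This stands. Repeated ANOVA, offered for secondary outcomes, and the perfusion mixed model can both carry it. The gap is limited to binary outcomes and the rank-based option. The per-breast ratings quoted from F2 are also optional.

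**The correlation is assumed, so the gain is too.** This stands as well. At zero correlation chi-square has slightly more power. G2 plans no interval for this outcome, so the interval comparison shows what would follow rather than a stated error. The one-week rule may leave fewer than 30 pairs, which would lower power further.

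**Stronger readings a reader might infer.** One is that the plan would produce false claims of benefit. On a yes/no score, rejection exceeds 5% only slightly at zero or mildly negative correlation and falls well below it when the correlation is positive. Another is that the count wording in G2 allows several linked incidents in one breast to be added up, which could inflate false positives. H1 points instead to one yes/no per breast: "CDO adjunct therapy will reduce the likelihood of surgical wound complication including dehiscence and its volume, infection or surgical revision". F2 likewise speaks of incidence, and the documents give no number of incidents per breast from which to size an effect. A third is that the estimated treatment difference is biased; on complete pairs it is unchanged.

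**Conclusion.** The complication analysis is wrong as written, because it ignores the pairing that the randomisation creates. The error lies in the p-value and in any interval, not in the estimated difference. At the assumed 10-15% rate with 30 pairs, chi-square is about nominal at zero correlation and increasingly conservative as the correlation rises. Asymptotic McNemar stays between 1.6% and 4.8% for correlations 0 to 0.6.

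That the test does not match the design follows from the documents alone. How much is lost depends on the assumed rate, effect and correlation. The point deserves correction because the outcome is primary, but its weight is moderate: this is an exploratory pilot sized on budget, and no test considered here gives a decisive answer on complications.

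**What to change.** Amend G2 as follows.

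1. Score each breast once, yes/no, for any wound complication by week 4. State whether scar size is a component: G2 lists it among the wound-related events, the corresponding list in F2 does not, and both lists are given as examples.
2. Report the within-patient risk difference with a 95% paired score (Tango) interval and the discordant-pair counts. Name the interval, because the simple paired Wald interval covers only 87% for 10% to 5% at correlation 0.4.
3. Replace chi-square with one prespecified McNemar test, and state alpha and sidedness. The asymptotic form agrees with the Tango interval. The exact form is a more conservative alternative and a legitimate preference, at the cost in power shown above.
4. For per-breast secondary outcomes, replace Mann-Whitney and chi-square with Wilcoxon signed-rank, a paired t-test or a model with a patient effect, and with McNemar if binary.

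**Cost.** Wording, plus one decision about the outcome definition; no new data or patients. Power for a halving of complications stays under 20% by each test calculated, and McNemar loses slightly if the correlation is zero. At correlation 0.4 under no effect, asymptotic McNemar cannot reject in 31% of trials at a 15% rate, and in 59% at 10%, because there are fewer than four discordant pairs. What is gained is an interval and test that match the design, so the result should be presented as estimation.

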Please note that subjects will be consented before performing any study related measurements. This study will not bring any direct costs to the subject. The subject's medical insurance will be billed for all standard of care procedures.

Eligible subjects will be internally randomized and will receive the intervention for 4 weeks. Each subjects will receive standard of care for wound treatment. Intervention side will receive adjunct Continuous Diffusion of Oxygen (CDO) therapy using a novel dressing, which facilitates continuous supply of oxygen to the wound inside the wound dressing using a portable device named OxyGeni . We will collect patient demographics (e.g., age, sex, height, weight, race, ethnicity, marital status, level of education, etc), relevant medical history (e.g., comorbidity, type of surgery, number of prescription and over counter medication, etc), and relevant social factors (e.g., marital status, years of education, type of work, tobacco history, etc) at baseline. Primary outcomes include tissue oxygenation (assessed using Kent Imaging system) and incidence of wound complications (e.g. dehiscence, infection, and surgical revision). Primary outcomes will be assessed at baseline and on a weekly basis for up to 4 weeks. Secondary and exploratory outcomes include inflammation (assessed using a KENT camera), pain (assessed visual analog scale). The secondary and exploratory outcomes will be assessed at baseline and week-4. Other optional assessments include quality of life (NIH Global Health PROMIS), depression (Center for Epidemiologic Studies Depression Scale, CES-D), cognitive function MoCA), and psychosocial metrics (e.g. fatigue, anxiety, frailty, sleep, etc). These assessments are optional and will be done upon time availability and patient acceptance. We anticipate that duration of all assessments will not exceed 60 minutes. We will be reviewing the billing records for our

patients to explore costs of both groups. We may visit the patient's home for an appointment that doesn't require the physician present or to fix any issues with the device.

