Is BCM the COORDINATING CENTER for this multi-site research? No or Not Applicable

Section I: Potential Benefits

Describe potential benefit(s) to be gained by the individual subject as a result of participating in the planned work.

There may be no direct benefit to the subject by being in this study. What the researchers find out from this study may help other people with surgical wound closures. This research utilizes a new dressing with active oxygen supply to the surgically closed wounds to reduce the likelihood of developing wound dehiscence.

Specialized wound dressings have the ability to improve specific physiological processes that facilitate healing. However, their specific benefits and target wounds is not well understood. Consequently, these are either underutilized in clinical

practice or over utilized without any well-defined criteria. OxyGeni oxygen delivery system is a novel wound healing therapy that promises to enhance vascular conditions at the wound bed and expediting wound healing.

Describe potential benefit(s) to society of the planned work.

There may be no direct benefit to the subject by being in this study. What the researchers find out from this study may help other people with surgical wound closures. This research utilizes a new dressing with active oxygen supply to the surgically closed wounds to reduce the likelihood of developing wound dehiscence, the main contributor to surgical revision.

Specialized wound dressings have the ability to improve specific physiological processes that facilitate healing. However, their specific benefits and target wounds is not well understood. Consequently, these are either underutilized in clinical practice or over utilized without any well-defined criteria. OxyGeni oxygen delivery system is a novel wound healing therapy that promises to enhance vascular conditions at the wound bed and expediting wound healing.

Do anticipated benefits outweigh potential risks? Discuss the risk-to-benefit ratio.

Although there some risks involved in this study associated with the device and some of the procedures involved, the study does provide the possibility of benefit to subjects. Therefore, the benefits outweigh the risks involved.

Section J: Consent Procedures

J1. Waiver of Consent

Will any portion of this research require a waiver of consent and authorization? Yes

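### G2 tests a number of complication incidents without saying that each breast counts once, so one failing wound can enter the chi-square more than once

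*Combined protocol and SAP*

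**What the plan says.** G2 (Data Analysis) is the only place that names a test for the complication outcome: "We will use chi-square to estimate whether the number of wound complication incidents is less in the intervention group compared to the control group". The same section describes that outcome as "incident of wound related adverse events (e.g., incident wound dehiscence, infection, scar size, and surgical revision"), and also lists scar size among the secondary outcomes. No section defines an incident, gives a denominator or says how a breast with several events is counted.

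Other sections use different words for the same outcome:

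- Section D, H1: "CDO adjunct therapy will reduce the likelihood of surgical wound complication including dehiscence and its volume, infection or surgical revision".
- F2 (Procedure): "incidence of wound complications (e.g. dehiscence, infection, and surgical revision").
- F1 (Design), Visits 1-4: "The status of wound closure and presence of wound complication will be monitored every week". The same paragraph has "weekly assessment up to 4 weeks or full wound healing or surgical revision, whichever comes first".
- Section I, on societal benefit, calls the target event "wound dehiscence, the main contributor to surgical revision".

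Side is randomised within each patient, so 30 patients give 30 treated and 30 control breasts. The documents state no significance level.

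**The concern.** A chi-square test assumes that each counted unit is independent of the others and appears once. If the count is of incidents, a breast that dehisces and is then revised contributes two events with a single cause. The variance that the test assumes is then too small.

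The numbers are small enough for this to matter. If the rate in Section C (10%-15%) applies per breast, the expected number of failing breasts per side is 30 × 0.10 = 3 to 30 × 0.15 = 4.5. Whether one wound counts once or three times can then change the result. An undefined unit also leaves the counting rule open until the data have been seen.

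**Working it through.** G1 bases the sample size on budget and feasibility, so the plan has no error rate or power figure to reproduce. The check asks how much the counting rule matters.

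**Inputs from the documents.** 30 breasts per side (G1, with within-patient allocation from Section D); complication rate 10%-15% (Section C, which does not say whether per breast or per patient; taken here as per breast).

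**Assumptions.** Nominal two-sided 5%; no treatment effect; number of incidents *m* in a failing breast; correlation ρ between a patient's two breasts.

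**Step 1: one illustrative data set.** Suppose 4 control breasts have 9 incidents in all and 2 treated breasts have 2.

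- Incidents, 1:1 chi-square: (9 − 2)² / (9 + 2) = 49/11 = 4.45, p = 0.035.
- Breasts, 4/30 versus 2/30: 60 × (4×28 − 2×26)² / (30×30×6×54) = 216,000/291,600 = 0.74, p = 0.39 (Fisher exact 0.67).

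The example is chosen to show that the rule can matter. It does not show how often it does.

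**Step 2: approximate inflation, independent breasts.** The variance of the incident difference is inflated by about E[m²]/E[m], and the rejection rate is about 2 × (1 − Φ(1.96/√ratio)).

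- 10% of failing breasts have two incidents: 1.3/1.1 = 1.18, about 7%.
- 20% have two: 1.6/1.2 = 1.33, about 9%.
- One, two or three incidents with probabilities 0.7, 0.2, 0.1: 2.4/1.4 = 1.71, about 13%.
- One, two or three equally likely: (14/3)/2 = 2.33, about 20%.

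This treats the number of failing breasts as Poisson and ignores discreteness, so it runs high.

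**Step 3: simulation.** 200,000 null trials per setting; pairs drawn with rate 10%, 12.5% or 15% and correlation ρ; 1:1 chi-square on incidents. Rejection in percent, range over the three rates:

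| Incidents per failing breast | ρ = 0 | ρ = 0.3 | ρ = 0.5 |
|---|---|---|---|
| Always one | 3.0-3.8 | 1.2-1.5 | 0.4-0.6 |
| 10% have two | 4.6-5.5 | 2.1-2.5 | 0.9-1.1 |
| 20% have two | 6.2-7.0 | 3.0-3.6 | 1.4-1.7 |
| 1/2/3 at 0.7/0.2/0.1 | 10.4-11.0 | 6.2-6.4 | 3.6-3.8 |
| 1/2/3 equally likely | 17.8-18.5 | 12.0-12.8 | 7.8-8.4 |

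The undefined denominator adds further spread. With exactly two incidents in every failing breast and ρ = 0, the 1:1 form rejects about 15% and incidents over 30 breasts up to 22%.

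**Step 4: each breast counted once.** An unpaired Pearson chi-square rejects 5.2%-5.6% at ρ = 0 and 0.8%-0.9% at ρ = 0.5. Exact McNemar rejects 1.0%-1.8% at ρ = 0 and 0.1%-0.5% at ρ = 0.5. Neither is materially inflated.

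**The case against.** A reader might infer that the plan counts one wound several times and that its false-positive rate is therefore well above 5%. The documents do not support that.

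- No section says that repeat or multiple events in one breast are counted separately. Likelihood (H1, G1), incidence (F2) and presence (F1) all fit a yes/no outcome, and G2's sentence on baseline comparisons pairs chi-square with binary variables.
- Recounting an open wound at successive visits is speculative. G2 speaks of incident dehiscence, which suggests new onset, and F1 ends weekly assessment at healing or revision.
- The documents give no distribution of incidents per breast. If a second incident is uncommon, there is little or no inflation. Ignoring the pairing makes the test conservative, which can offset inflation in part or in full.
- This is a pilot with two primary outcomes, no stated significance level and no confirmatory decision rule.

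All of this limits the claim, and none of it closes the gap. The softer words sit in a hypothesis, a sample-size rationale, an outcome label and a visit description, while the sentence that specifies the test refers to a number of incidents. Stopping at revision does not remove a dehiscence already recorded. Two departures that may cancel by an unknown amount do not control error, and correcting only the pairing would leave the counting problem in place.

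**Conclusion.** The concern holds as a defect of specification. As worded, G2 allows one failing wound to supply several events to a chi-square, and the test is not valid if that happens. The rest of the protocol points to one yes/no value per breast, so G2 should be brought into line with it.

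The size is conditional. Under a nominal two-sided 5% level, 30 breasts per side and a 10%-15% per-breast rate, the 1:1 chi-square on incidents rejects about 5%-7% when 10%-20% of failing breasts have a second incident and about 10%-19% under the two heavier distributions, with independent breasts. At ρ = 0.5 the range across all four is about 1%-8%. The documents fix neither the multiplicity nor the correlation, so no single error rate can be attributed to the plan.

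**What to change.** In G2, replace the incident count with this definition: breast with at least one dehiscence, infection or surgical revision from surgery to week 4 (yes/no, each breast counted once). Compare the two breasts of each patient with a paired test, for example exact McNemar. Tabulate the components and any repeat incidents descriptively by side. State that scar size, which G2 lists in this outcome, is analysed separately as the secondary outcome it already is.

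The cost is a short edit to G2 and no new data. There are two downsides. Multiple events in one breast no longer add weight, which is why the descriptive table is needed. Exact McNemar is also conservative at this size: it needs at least six discordant patients, all in one direction, for p < 0.05 (2 × 0.5⁶ = 0.031; with five, 2 × 0.5⁵ = 0.0625). The paired difference and its confidence interval should therefore be reported alongside the p-value.
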